3. RESEARCH PROTOCOL

3A. DESCRIPTION OF STUDY POPULATION, INCLUSION AND EXCLUSION CRITERIA

Study Sites. [name] has a strong relationship with the Chatham County School District (See Letter of Support). There are 8 middle schools in the District, with a combined enrollment of 712 7th graders. The schools are diverse in terms of race and income: 47% are racial/ethnic minority (e.g., 31.5% are Black) and 69% are receiving free or reduced cost lunch. We will randomly select three schools. Should a school choose to opt out, we will randomly select another from the remaining five schools. Note that, while enthusiasm for the program is high, it is against district policy to allow principals to provide Letters of Support.

Should additional sites be needed, we will draw upon local Boys & Girls Clubs. The Boys & Girls Club of America (BGCA) includes over 4,000 clubs in the U.S. and serves approximately 4 million young people. Local clubs affiliated with the BGCA provide young people with a safe, supervised, and constructive environment during non-school hours. The organization serves a diverse population of young people with a large representation from low-income backgrounds. The Boys & Girls Clubs of Durham and Orange Counties serve students in the cities of Durham and Chapel Hill. The clubs are diverse in terms of race and income: 85% are African American, 6% Hispanic, 3% are White, 3% are Asian, 2% are Multiracial, and 1% are American Indian/Alaskan Native. About 62% of students are experiencing financial hardship, 1% have disabilities, and 4% are English Language Learners.

We also may recruit 13-14 year olds using advertisements on social media, such as Facebook and Instagram.

Youth eligibility criteria. The inclusion criteria for youth matches the anticipated profile of users when the program is publicly available in the future. Participants will: be enrolled in one of our partner schools, be in middle school (i.e., 7th or 8th grade) or between the ages of 12-14 years of age, be English-speaking, own their own cell phone, intend to have the same cell phone number for at least 3 months (this may or may not apply, depending on the number of youth who meet this criterion), provide informed written assent, and have parental permission. Non-English speakers and youth who do not have the reading ability to complete the screener are not eligible.

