Integrating lessons learned into the content. Several participants in the beta test expressed confusion regarding the interactive Text Buddy feature. Further probing revealed that some of this was related to feelings of discomfort about discussing bullying with students they went to school with. Nonetheless, beta test participants sent between 0-52 messages to their Text Buddy, suggesting its acceptability potential. To improve the experience, we will expand the instructions for the Text Buddy feature and include more concrete prompts about what Buddies can talk about with each other (e.g., Maybe text your buddy and talk about what you think it would be like if you stood up for a friend being bullied at school tomorrow). We also will match youth with someone at a different school/setting and make sure that they are aware of this so they do not worry they are talking with a classmate they may know.

Drafting attention matched control content. In the beta test, the control group received two messages a week focused on thanking them for being in the study. As has been done in [name] other interventions (e.g., R21 CA135669; R34MH109296), we will draft attention-matched content to well position this R21 for a competitive R01 submission. To ensure that youth in both arms receive the same 'attention,' content will address healthy lifestyle topics unrelated to bullying (e.g., fitness, nutrition).

Confirming adapted content for acceptability in Content Advisory Teams (CAT; n=70). The content will next be reviewed by a CAT comprised of ~24 students. Each CAT member will have one week to review the messages and provide feedback through an online platform. Next, an online group discussion will elicit reactions to the messages and program design. Possible questions include: How well do these messages speak to the experiences you and your friends have around bullying? How clear do you find the messages? How could we say things differently to make the messages more understandable? Once feedback from the CAT has been integrated, a second 24-member CAT of different students will confirm that the content has been improved. For instance, in a previous intervention development [name]'s team led, the second CAT noted that we included too many emojis, which we had added based upon feedback from the first CAT. Having two different groups review the content also ensures a wider range of opinions and feedback. The control content will be reviewed by a ~24-member CAT.

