validated survey question has been used successfully in [name] up with Media survey, which included youth as young as 10 years old.⁷⁸ 4) **Exposure to community violence:** Four JVQ questions will measure exposure to community violence (e.g., Have you ever seen someone get attacked or hit on purpose?).⁷⁷ 5) **Alcohol use:** We will use the YRBS question to measure alcohol use in the past year and in the past 30 days.⁷⁹ 6) **Literacy** will be measured with the Comprehension subscale of the Stanford Diagnostic Reading Test⁸⁰. It was designed to be used by students with low literacy and has high internal validity ($\alpha = .84-.90$)⁸¹. And 7) **Demographic characteristics:** Sex assigned at birth, gender identity, sexual identity, age, grade, cell phone number, and number of people living in the home; length of time using text messaging, length of time with current cell phone number, and average text messaging frequency. **Data analysis is described in Statistical Design and Power.**

The reliance on youth self-report bears discussion. We have carefully considered the potential benefits and drawbacks of including teacher report. We decided not to because middle adolescents, those who are 12-14 years of age and typically in middle school, teachers see their students for one class a day. They are unlikely to know everything that occurs during a student's day and whether they are bullying or being bullied in other classrooms. We decided not to collect parent report because parents rarely know about their child's bullying behavior.⁸²

Scientific rigor of the experimental design, methods, and analyses. The rigor of the proposed study is high. For example, random assignment eliminates the possibility of youth being purposefully assigned to a particular study arm. The attention-matched control will reduce the likelihood that behavior change, if detected, is due to the 'attention' youth received by the daily text messages. Program fidelity will be high as the sending of messages is automated and the same for each student.

3E. STATISTICAL DESIGN AND POWER

Specific Aim 1: Finalize the BullyDown program.

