Monitoring of Text Buddy Communication. Text Buddies are paired intervention participants who will be encouraged to text message each other about to discuss program content throughout the intervention. For example: “Talking about your bullying experiences with friends can be hard. Now that you’re equipped with mad communication skills, try talking with your Buddy about the most recent time you saw someone bullied. What did you do? How did you feel? Text your Buddy and share.”

Buddies will be paired based on sex and school / setting so that they will be at different schools / settings based upon findings from the earlier beta test. The software program will identify youth who match on these criteria and automatically pair them. Those who are not automatically paired will be flagged so that the research team can manually pair youth.

We posit that social support from a Text Buddy will positively influence youth over time. However, balancing this with the privacy needs of our participants, who likely do not want to exchange contact information with a stranger, is important. As such, all Text Buddy messages are routed through the study server, replacing the need for this exchange. Participant cell phone numbers will never be distributed to other participants. To send a message, participants will simply text the dedicated BuddyLine, the program phone number that participants will use to communicate with their Buddy. This message is sent directly to the program server, which identifies the intended recipient, and routes the message to the assigned Text Buddy. This methodology will also allow us to measure the amount of interaction between Buddies accurately; if participants texted each other directly, we would have to rely on self-report to measure frequency of contact. For analysis, we will keep a count record to reflect the number of messages sent by each participant.

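### Text Buddies are separated by school or setting, but the stated aim is to avoid pairing schoolmates; the rule should compare school attended across all recruitment routes

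*Combined protocol and SAP*

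**What the plan says.** The pairing rule is in Section 4.b, under Monitoring of Text Buddy Communication: "Buddies will be paired based on sex and school / setting so that they will be at different schools / settings". Software applies it. Youth whom the software cannot match are flagged and paired by the research team, with no separate criterion stated for that step.

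The purpose is in Section 3C, Specific Aim 1, under the lessons learned from the beta test. Part of the confusion about the Buddy feature was traced to "feelings of discomfort about discussing bullying with students they went to school with". The remedy is to match youth with someone at a different school or setting and to "make sure that they are aware of this so they do not worry they are talking with a classmate they may know".

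Section 3A describes three recruitment routes:

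- Schools in the Chatham County district.
- Clubs, if more sites are needed. Clubs "provide young people with a safe, supervised, and constructive environment during non-school hours". On location: "The Boys & Girls Clubs of Durham and Orange Counties serve students in the cities of Durham and Chapel Hill".
- Social media: "We also may recruit 13-14 year olds using advertisements on social media, such as Facebook and Instagram".

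The eligibility list in Section 3A says that participants will "be enrolled in one of our partner schools" and does not limit this to the school route.

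**The concern.** The purpose concerns the school a youth attends, whereas the rule is written in terms of school or setting. The two coincide when everyone is recruited through a school. They can part once a participant is identified by a Club or by an online route, because Club members and 13-14 year olds found through advertisements also go to school.

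What is at stake is participant protection and the Buddy feature itself. Section 4.b prompts youth to tell their Buddy about the most recent time they saw someone bullied, and Section 4.a lists harmful Buddy conversations among the risks. A youth who has been reassured about classmates could disclose such an episode to a schoolmate. Acceptability is a main outcome in Table 3, whose example scale item asks whether participants liked their Text Buddy, so the remedy for the beta-test discomfort ought to work on every recruitment route.

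**Working it through.** The documents give no figure to reproduce. The check is to apply the written rule to each type of pair that the recruitment routes allow.

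| Pair | Does a different school or setting ensure a different school? |
|---|---|
| Recruits from two different schools | Yes. |
| School recruit and Club recruit | Not by the rule. Overlap may be rare, since the district is Chatham County and the named Clubs serve Durham and Chapel Hill. |
| Recruits from two different Clubs | No. Two Clubs may draw on one school. |
| School recruit and social-media recruit | No. The online recruit may attend the recruited school; no geographic limit is stated for this route. |
| Club recruit and social-media recruit | No, for the same reason. |
| Two social-media recruits | Undefined. The plan does not say whether they share a setting. |

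The likelier routes to a schoolmate pair are therefore two Clubs sharing a school, and a social-media recruit who attends a recruited school.

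**Is school attended compared anywhere?**

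- Pairing (Section 4.b): sex and school or setting only. No criterion is given for manual pairing.
- Minimization (Section 3C): the possible factors include school or Club, but this governs allocation to arms, not pairing.
- Demographic items (Section 3D): "Sex assigned at birth, gender identity, sexual identity, age, grade, cell phone number, and number of people living in the home", followed by texting history. School attended is not listed. Club is not listed either, nor is school for school recruits, although other sections use both. The list therefore does not show that school goes unrecorded.
- Eligibility (Section 3A): if partner-school enrollment applies to every route, someone must ascertain the school, but nothing says that pairing uses it.

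**Can the frequency be bounded?** The intervention arm has 76 youth, so at most 76/2 = 38 pairs. Let m be the number of pairs that include a Club or social-media recruit, and q the chance that such a pair shares a school. Neither is in the documents. Treating pairs as independent, the chance of at least one schoolmate pair is 1 − (1 − q)^m. For purely assumed values:

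| q (assumed) | m = 10 | m = 38 |
|---|---|---|
| 0 | 0% | 0% |
| 0.5% | 4.9% | 17.3% |
| 1% | 9.6% | 31.7% |
| 2% | 18.3% | 53.6% |
| 5% | 40.1% | 85.8% |

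For example, m = 10 and q = 1% gives 1 − 0.99^10 = 9.6%. The span from 0% to 85.8% reflects what is unknown. It is not an estimate.

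**The case against.** The strongest reply is that the rule may already do what is wanted. The slash is undefined and can be read as requiring both school and setting to differ. The word setting was presumably included because other routes exist. On that reading only the wording is unclear. This stands in part: the plan may intend the right check, but it does not say so, and it does not say where the school of a Club or social-media recruit would come from.

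Other points on that side also stand:

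- Section 3A makes Clubs conditional on need and says social media may be used. Section 3C is firmer, saying that recruitment will also run through both, but the routes may contribute few youth.
- Friend referral is ruled out on the social-media route, which removes one source of schoolmates.
- Messages pass through the study server without sharing numbers. There is a Code of Conduct, keyword blocking, staff monitoring and escalation to the PI. Section 4.b reports no inappropriate Buddy interactions in the beta test and no case of one Buddy bullying another across three projects. These limit harm, but they act after a pair has been formed.

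Three stronger readings are tempting, and the documents support none of them:

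- *Pairing is unable to check school.* Screener and enrollment items are not reproduced, and the demographic list is no evidence either way.
- *Youth are promised that a Buddy can never be a classmate.* They are to be made aware of the different school or setting. Easing worry about classmates is the stated purpose, not quoted wording.
- *A schoolmate rate follows from the number of partner schools.* That needs every Club recruit to attend a partner school, an even spread across schools and a known number of Club recruits. The last two are not given, and the first relies on a literal reading of the eligibility list that sits uneasily with the different catchments.

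**Conclusion.** The point holds as a gap between a rule and its own stated purpose. If Clubs or social media are used, a different setting does not guarantee a different school, and the plan does not state that school attended is compared across routes in either software or manual pairing.

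The frequency cannot be estimated from the documents and may be zero. The conclusion does not depend on any assumed rate. It rests on the wording of the rule and on the fact that Club and social-media recruits of this age attend schools. A reader might also infer that a victim is likely to be paired with the perpetrator, or that acceptability will fall. Neither follows: each needs further steps for which the plan has no data.

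No outcome definition, sample size, error rate or analysis changes. Severity is low; this is a cheap improvement that serves the rule's own aim.

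**What to change.** Three linked changes:

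1. Record the school attended for every RCT participant before pairing, whatever the recruitment route.
2. In Sections 3C and 4.b, state the pairing condition as same sex and different school attended, for both software and manual pairing. Keep recruitment setting as a secondary criterion, and say how two social-media recruits are treated.
3. Make the wording given to youth match what is actually checked.

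It would also help to state in Section 3A whether partner-school enrollment applies to Club and social-media recruits.

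The cost is one screener or baseline item and one pairing condition. A few more youth may need manual pairing. Section 3C already notes that pairing across schools or settings may make full randomization difficult in the new beta test, so the software should be checked with the revised condition before the RCT starts.
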